## Subgroup analyses

Planned sub-group analyses will assess consistency across subgroups of differences between TXA and placebo arms with respect to the primary outcome in the intention to treat population only. These will be assessed using regression models with interaction term(s) between the particular subgroup and treatment arm. These analyses will provide a risk ratio

and confidence interval for the effect of randomised arm in each subgroup and the interaction p-value. The subgroup variables are:

- Age, dichotomised to >= 50 years
- Time from injury to first dose (<1 hour, 1-<2 hours, 2-<3 hours, >=3 hours)\*
- First valid recorded systolic blood pressure categories (<=75, 76–89, >=90 mm Hg)
- Mechanism of trauma (penetrating, blunt, blast/burns\*)
- Baseline GCS<9.

\*If there are <10 patients in any single category then this category will be tabulated but not included in the regression modelling.

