## Secondary Objectives:

(1) To determine the effect of early administration of TXA, compared to placebo, on coagulation and fibrinolysis, and on clinical outcomes that are mediated through other putative inflammatory, immune, and neurological effects of plasmin.

(2) To determine whether early administration of TXA, compared to placebo, is associated with excessive vascular occlusive events, especially among potentially higher risk patients (e.g., aged >50 years old).

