# Secondary outcomes

- 1. Units of blood products used (packed red blood cells, fresh frozen plasma, platelets, prothrombin complex concentrate, recombinant factor VIIa, cryoprecipitate) in the first 24 hours
- 2. Blood lactate concentration at patient arrival to hospital
- **3.** Coagulation profile (international normalised ratio, activated partial thromboplastin time, fibrinogen, platelet count) at:
  - a. hospital arrival;
  - b. end of treatment with study drug (i.e., immediately after administering the second dose of the study drug by 8-hour infusion);
  - c. 24 hours after the first dose of study drug.
- **4.** Vascular occlusive events (deep venous thrombosis, pulmonary embolism, myocardial infarction, stroke) up until 28 days or hospital discharge (whichever occurs first).
- 5. Ventilator-free days in first 28 days.
- 6. Mortality at:
  - a. 24 hours;
  - b. 28 days;
  - c. 6 months.
- 7. Proportion of deaths due to:
  - a. bleeding;
  - b. vascular occlusion (pulmonary embolus, stroke or acute myocardial infarction);
  - c. multiorgan failure;
  - d. brain/neurological injury.
- **8.** Cumulative incidence of sepsis up until 28 days or hospital discharge (whichever occurs first).
- **9.** Quality of life (World Health Organisation Disability Assessment Schedule (WHODAS) 2.0 and EuroQol 5-Dimension (EQ-5D)) at 6 months.

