# Secondary and tertiary endpoint analyses

The binary secondary outcomes of vascular occlusive events (#4), mortality at 24 hours, 28 days and 6 months (#6) and incidence of sepsis to 28 days (#8) will be analysed using the same log-binomial regression modelling approach as the primary outcome. Cumulative mortality to 6 months will also be displayed with Kaplan-Meier curves. Blood product usage (#1) will be dichotomised as any/none and also analysed with log-binomial regression. The quantity of blood product usage among patients receiving the product will be summarised with medians and interquartile ranges, and compared between treatment groups using quantile (median) regression, reporting the difference in medians between treatment arms together with 95% Cls and p values. Analyses of blood lactate concentration (#2) (regardless of assay method) and coagulation profile variables at each time point (#3) will similarly use quantile regression to compare medians between treatment groups. Blood lactate concentration (#2) obtained by venous and arterial samples will each also be dichotomised at >3mmol, and a composite measure of >3mmol for either sampling method will be calculated. INR (#3) will be dichotomised at >1.3 IU, and fibrinogen (#3) at <1 g/L and at <2 g/L. These dichotomised variables will be analysed as binary variables as above. Ventilator-free days in the first 28 days (#5) will assign a value of 0 to patients dying within 28 days regardless of location at time of death, and a value of 28 days if never ventilated in ICU or never admitted to ICU. This will be analysed using quantile regression to estimate the difference in median ventilation-free days. The 4 causes of death (#7a,b,c,d) in patients that died at any time up to 6 months will be tabulated and reported descriptively. The cumulative incidence of each cause of death to 6 months will be displayed graphically taking into account the other competing causes of death, and with cause-specific hazard ratios estimated using Cox regression with censoring at the time of all other causes of death. A composite cause of 'potentially preventable death' will be calculated as any of bleeding, vascular occlusion and multi-organ failure. Comparison of median quality of life outcomes at 6 months (#9) between treatment arms will be analysed using quantile regression, with patients not alive at 6 months treated as having missing values (and see below), and with EQ-5D calculated using Australian weights (3).

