
Additional analyses of each of the vascular occlusive events (#4) and sepsis (#8) at 28 days will be performed to take into account the competing risk of death. This will use cumulative incidence functions with estimated incidence at 28 days, with the incidence compared across treatment groups using risk ratios with 95% CIs derived using the delta method. For analysis of quality of life outcomes at 6 months, for patients not alive at that time a value of 0 will be imputed for the EuroQol 5-Dimension (EQ5D) summary and VAS scores (3). For the WHODAS scale, in the absence of published guidelines for addressing mortality, a score of 61 will be imputed, placing death as worse than the maximum scale score of 60. These modified quality of life outcomes will also be analysed using quantile regression. Supplementary analyses of these outcomes will use inverse probability of death weighting rather than imputation of values to accommodate truncation by death.

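### The higher-risk part of secondary objective 2 (vascular occlusive events in, for example, older patients) has no planned analysis, because every subgroup analysis is limited to the primary outcome

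*SAP*

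**What the plan says.** SAP, Secondary Objectives, item 2, has two parts. The first is general: "To determine whether early administration of TXA, compared to placebo, is associated with excessive vascular occlusive events". The second singles out a population: "especially among potentially higher risk patients (e.g., aged >50 years old".

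SAP, Secondary outcomes, item 4, defines the endpoint: "Vascular occlusive events (deep venous thrombosis, pulmonary embolism, myocardial infarction, stroke) up until 28 days or hospital discharge", whichever comes first.

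SAP, Secondary and tertiary endpoint analyses, gives this endpoint two analyses. As a binary outcome it "will be analysed using the same log-binomial regression modelling approach as the primary outcome". Then, to allow for death as a competing risk, "Additional analyses of each of the vascular occlusive events (#4) and sepsis (#8) at 28 days will be performed", using cumulative incidence functions compared between arms. Neither analysis has an age term, an age stratum or any other risk grouping.

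SAP, Subgroup analyses, lists five subgroup variables, among them "Age, dichotomised to >= 50 years". It fits treatment-by-subgroup interactions, but only "with respect to the primary outcome in the intention to treat population only".

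**The concern.** The objective names a safety question about a particular kind of patient, and the analysis sections never look at that kind of patient for that outcome. The protocol could not fill the gap silently, because the SAP's own restriction of subgroup analyses to the primary outcome rules out the analysis that the objective calls for.

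Two things are at stake. A harm concentrated in older patients would be averaged with a null effect in younger patients, so the overall risk ratio would understate it. And an age-specific result produced after unblinding, whether reassuring or alarming, would be post hoc and open to the charge of selective reporting.

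A smaller mismatch goes with it. The objective's example is age above 50 and the subgroup list uses 50 and above, so patients aged exactly 50 fall on different sides.

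**Working it through.** **1. Objective against analysis**

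| Part of objective 2 | Planned analysis of outcome 4 | Answered? |
|---|---|---|
| Excess events, TXA v placebo, all patients | Log-binomial risk ratio; cumulative incidence at 28 days with death as competing risk | Yes |
| Excess events in higher-risk patients (example: age over 50) | None; age interaction planned for favourable GOSE only | No |

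The GOSE interaction by age is no substitute. Favourable GOSE combines death and severe disability from any cause, so it does not isolate thrombotic harm.

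**2. The plan's own figure**

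The number per arm used below comes from SAP, Sample size. For 60% v 69%, two-sided 5%, 90% power and pooled variance:

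n = [1.96·√(2·0.645·0.355) + 1.2816·√(0.60·0.40 + 0.69·0.31)]² / 0.09² = 592 per arm.

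With 10% loss, 592/0.90 = 657.8, so 658 per arm. Both stated figures reproduce. They concern GOSE and say nothing about precision for vascular occlusive events.

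**3. Illustration of size (assumed inputs)**

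The SAP gives no vascular occlusive event rate, no age distribution and no expected harm. The assumptions are a true risk ratio of 1.5 in older patients, a placebo risk of 5% to 15% in them, and 30% to 50% of 658 per arm in the older group. The formula is

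SE(log RR) = √[(1−p₁)/(n·p₁) + (1−p₀)/(n·p₀)], with 95% CI = RR × exp(±1.96·SE).

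95% CI around an older-group risk ratio of 1.5:

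| Share older (n per arm) | Placebo risk 5% | 10% | 15% |
|---|---|---|---|
| 30% (197) | 0.69–3.28 | 0.88–2.56 | 0.98–2.29 |
| 40% (263) | 0.76–2.95 | 0.94–2.38 | 1.04–2.16 |
| 50% (329) | 0.82–2.75 | 0.99–2.27 | 1.08–2.08 |

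The interval excludes 1 in only two of the nine cells.

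**4. Dilution and interaction at one of those points**

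Take 40% older with 15% placebo risk and RR 1.5, and 60% younger with 6.7% placebo risk and RR 1.0.

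- Overall TXA risk: 0.4·0.225 + 0.6·0.067 = 0.130.
- Overall placebo risk: 0.4·0.15 + 0.6·0.067 = 0.100.
- Overall RR = 1.30, SE = 0.154, 95% CI 0.96 to 1.76.
- Older group (263 per arm): RR = 1.50, SE = 0.186, 95% CI 1.04 to 2.16; power about 59%.
- Younger group (395 per arm): RR = 1.00, SE = 0.266.
- Ratio of risk ratios = 1.50, SE = √(0.186² + 0.266²) = 0.324, 95% CI 0.79 to 2.83; z = ln(1.5)/0.324 = 1.25, p about 0.21, power about 24%.

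**5. What an interaction test could detect**

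Across the same ranges, with a common event risk in both age groups and both arms for the variance, the ratio of risk ratios detectable with 80% power is about 2.1 to 4.4.

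**The case against.** The strongest reply is that objective 2 is, first of all, about excess events overall, and the SAP gives that question two proper analyses. A reader might infer that the whole safety objective goes unanswered. The documents do not support that, because the gap is confined to the higher-risk clause.

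Age over 50 is also only an example, so the SAP is not bound to that group. This is true, but no other higher-risk group is analysed for this outcome either.

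A further reply is that the analysis would be weak. This stands as a limit on what can be claimed. A reader might infer from the contrast between 1.30 (0.96 to 1.76) and 1.50 (1.04 to 2.16) that the missing analysis would reveal a harm that the planned one hides. That contrast rests on one assumed set of inputs. At a 10% placebo risk, or with 30% of patients in the older group, the older-group interval includes 1, and the interaction would probably be inconclusive throughout. Low precision is a reason to present the result as estimation. It does not justify leaving part of a stated safety question without a planned estimate.

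Two points limit the seriousness. The age cut at 50 is already pre-specified for GOSE, so a later split of this outcome need not use a data-driven cut, although the analysis itself would still be post hoc. And the difference between above 50 and 50-and-above affects only patients aged exactly 50, so it is a matter of wording.

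**Conclusion.** The point holds for the higher-risk clause of secondary objective 2 and for nothing wider. The SAP sets a question about vascular occlusive events in higher-risk patients and then, by restricting subgroup analyses to the primary outcome, plans no analysis that addresses it. This conclusion follows from the text and needs no assumed figure.

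The consequence can only be illustrated. A harm confined to older patients is diluted in the overall estimate whatever the inputs, but how much, and whether any interval would exclude 1, depends on event rates and an age split that the SAP does not give. Over the ranges assumed, the older-group interval around 1.5 runs from 0.69–3.28 to 1.08–2.08.

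It should be fixed, but it is not critical. The primary analysis, the sample size and the error control of the primary test are untouched.

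**What to change.** Extend the pre-specified age-by-treatment log-binomial model to secondary outcome 4. Report the risk ratio with 95% CI in each age group and the interaction, ideally with the competing-risk cumulative incidence by age group as well. Amend the scope sentence in Subgroup analyses to match. State that this is low-powered estimation and not a powered test, and that a non-significant interaction is not evidence of equal safety. Use one age cut, either above 50 or 50 and above, in both the objective and the subgroup list.

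If the sponsor does not want the analysis, removing the higher-risk clause from the objective would also reconcile the text, but the question would then go unanswered.

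The cost is one additional model and one table. No new data are needed, since age and outcome 4 are already analysis variables. The downside is one more low-powered subgroup comparison in a plan that makes no multiplicity correction. The change should be dated before unblinding; if that has passed, the analysis should be reported as post hoc.

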## **PUBLICATION PLAN**

The principal manuscript will analyse all endpoints apart from the quality of life secondary endpoints #9. These will be analysed in a separate manuscript.

## CHANGELOG

Version 1.0. August 19 2022.

